2.3. Final Analysis

After all subjects have completed the study, outstanding data queries have been resolved, and the database has been cleaned and finalized, the final analysis of the data will be performed.

3. GENERAL CONSIDERATIONS FOR DATA ANALYSES

Analysis results will be presented using descriptive statistics. For categorical variables, the number and percentage of subjects in each category will be presented; for continuous variables, the number of subjects [n], mean, standard deviation [SD] or standard error [SE], median, first quartile [Q1], third quartile [Q3], minimum, and maximum will be presented.

Statistical tests will be two-sided and performed at the 5% significance level unless otherwise prespecified in Section 6.1.

Data collected in the study will be presented in by-subject listings for all subjects in the Safety Analysis Set, unless otherwise specified. All by-subject listings will be presented by region and subject identification (ID) number in ascending order, unless otherwise specified.

3.1. Analysis Sets

Analysis sets define the subjects to be included in an analysis. Analysis sets and their definitions are provided in this section. The number of subjects eligible for each analysis set will be provided. Subjects who were excluded from each analysis set will be summarized or provided in a by-subject listing with reasons for exclusion by region.

3.1.1. All Enrolled Analysis Set

The All Enrolled Analysis Set includes all subjects who were enrolled in the study. Subjects are grouped within the All Enrolled Analysis Set by genotype (GT) and region.

3.1.2. Full Analysis Set

The Full Analysis Set (FAS) includes all subjects who were enrolled into the study and received at least 1 dose of study drug. The study drug in this study is SOF/VEL. Subjects are grouped within the FAS by region and genotype.

This is the primary analysis set for efficacy analyses.

3.1.3. Safety Analysis Set

The Safety Analysis Set includes all subjects who were enrolled into the study and received at least 1 dose of study drug. Subjects are grouped by region.

This is the primary analysis set for safety analyses.

3.2. Subject Grouping

For analyses based on All Enrolled Analysis Set and Full Analysis Set, subjects will be grouped by region for primary analysis of the primary endpoint and grouped by region and genotype for all other analyses. Unless otherwise specified, groups by genotype include GT1a, GT1b, GT1 (Total), GT2, GT3, GT4, GT5, GT6, Indeterminate, and Total, and groups by region include Region 1, Region 2, and Overall. For analyses based on the Safety Analysis Set, subjects will be grouped by region and genotype for demographic information and grouped by region for all other safety analyses.

3.3. Examination of Subject Subsets

Subject subsets will be explored for the primary efficacy endpoint, SVR12. The subject subsets include the following:

- age (< 65 years, ≥ 65 years)
- sex (male, female)
- baseline body mass index (BMI) (< 25 kg/m², ≥ 25 kg/m²)
- baseline HCV RNA (< 800,000 IU/mL, ≥ 800,000 IU/mL; < 5 log₁₀ IU/mL, ≥ 5 log₁₀ IU/mL)
- baseline ALT (≤ 1.5 × upper limit of normal [ULN], > 1.5 × ULN)
- IL28B (CC, non-CC; with non-CC further broken down to CT, TT)
- cirrhosis (presence, absence, missing)
- prior HCV treatment experience (treatment naïve, treatment experienced)
- prior HCV treatment (DAA+PEG+RBV, INTERFERON+RBV, PEG+RBV, Other) for treatment-experienced subjects
- most recent HCV treatment response (non-responder, relapse/breakthrough, early treatment discontinuation, met a virologic stopping rule, not otherwise listed, unknown) for treatment-experienced subjects
- adherence to study regimen (<80%, ≥ 80%)

3.4. Missing Data and Outliers

3.4.1. Missing Data

In general, missing data will not be imputed unless methods for handling missing data are specified.

For missing last dosing date of study drug, imputation rules are described in Section 3.7.1. The handling of missing or incomplete dates for adverse event (AE) onset is described in Section 7.2.5.2, and for prior and concomitant medications in Section 7.5.

For analyses of categorical HCV RNA data, missing posttreatment HCV RNA data will have the missing data imputed. Missing on-treatment HCV RNA will have the missing data imputed up to the time of the last dose (for on-treatment displays). If the study day associated with the last dosing date is greater than or equal to the lower bound of a visit window, and the value at the visit is missing, the value will be imputed. If the study day associated with the last dosing date is less than the lower bound of a visit window then the on-treatment value at that visit will remain missing.

If a HCV RNA data point is missing and is preceded and followed in time by values that are “< LLOQ target not detected (TND)”, then the missing data point will be set to “< LLOQ TND”. If a data point is missing and preceded and followed by values that are “< LLOQ detected”, or preceded by “< LLOQ detected” and followed by “< LLOQ TND”, or preceded by “< LLOQ TND” and followed by “< LLOQ detected”, then the missing value will be set to “< LLOQ detected”. In these situations the data point will be termed a bracketed success; otherwise, the data point will be termed a bracketed failure (ie, \geq LLOQ detected). If a data point is missing and is not bracketed, the missing data point will also be termed a failure (ie, \geq LLOQ detected) except for SVR24, which will be imputed according to SVR12 status. Success for SVR12 who have no further HCV RNA measurements collected will be counted as a success for SVR24 due to the high correlation between these 2 endpoints.

For the analyses of continuous HCV RNA efficacy data, when and only when a missing HCV RNA value is imputed as < LLOQ TND or < LLOQ detected according to the imputation rule described above, the corresponding continuous value will be imputed to LLOQ – 1 IU/mL. No other imputation will be performed for continuous HCV RNA data.

For health-related quality of life data SF-36, missing data will not be imputed.

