3.7.3. Selection of Data in the Event of Multiple Records in an Analysis Window

Depending on the statistical analysis method, single values may be required for each analysis window. For example, change from baseline by visit usually requires a single value, whereas a time-to-event analysis would not require 1 value per analysis window.

If multiple valid nonmissing numeric observations exist in an analysis window, records will be chosen based on the following rules if a single value is needed:

- For baseline, the last available record on or prior to the date of the first dose of study drug will be selected. If there are multiple records with the same time or no time recorded on the same day, average (arithmetic mean) will be used for the baseline value. If multiple ECG measurements occur on the same day prior to first dose of any study drug, the average will be used considered as baseline value for continuous data, regardless of the timing of these multiple ECG measurements.

- For postbaseline visits:
 - The record closest to the nominal day for that visit will be selected except for HCV RNA posttreatment follow-up visits, for which the latest record in the analysis window will be selected.
 - If there are 2 records that are equidistant from the nominal day, the later record will be selected.
 - If there is more than 1 record on the selected day, the average will be taken, unless otherwise specified.

If multiple valid nonmissing categorical observations exist in a window, records will be selected as follows:

- For baseline, the last available record on or prior to the date of the first dose of study drug will be selected. If there are multiple records with the same time or no time recorded on the same day, the value with the lowest severity will be selected (eg, normal will be selected over abnormal). If multiple ECG measurements occur on the same day prior to the first dose of any study drug, the value with the lowest severity will be selected regardless of the timing of these multiple ECG measurements.
- For postbaseline visits, follow the same rules described above for postbaseline numeric observations, except that if there are multiple records on the same day, the most conservative value will be selected (eg, abnormal will be selected over normal).

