4. SUBJECT DISPOSITION

4.1. Subject Enrollment and Disposition

A summary of subject enrollment will be provided for each investigator. The summary will present the number and percentage of subjects in the Safety Analysis Set. The denominator for the percentage calculation will be the total number of subjects analyzed.

A summary of subject disposition will be provided by region and genotype. This summary will present the number of subjects screened, the number of subjects enrolled, the number of subjects enrolled but never treated, and the number and percentage of subjects in each of the categories listed below. For the “Treated” category, the denominator for the percentage calculation will be the total number of subjects enrolled for each column. For all other categories, the denominator for the percentage calculation will be the total number of subjects in the Safety Analysis Set for each column.

- Treated (Safety Analysis Set)
- In FAS
- Continuing study treatment if applicable
- Completed study treatment
- Did not complete study treatment with reasons for premature discontinuation of study treatment
- Completed study
- Did not complete the study with reasons for premature discontinuation of study

Among subjects who completed study treatment and who discontinued study treatment, the number and percentage of subjects will be summarized for:

- Who had no HCV posttreatment Week 4 assessment and thereafter (No HCV FU-4 and thereafter)
- Who had HCV posttreatment Week 4 assessment but no HCV posttreatment Week 12 assessment and thereafter (With HCV FU-4 but No FU-12 and thereafter)

If a subject did not have any HCV RNA assessment ≥ 21 days after the last dose of any study drug (ie, lower bound of FU-4 visit for HCV RNA data), the subject is categorized as having “No HCV FU-4 and thereafter”. If a subject had the HCV FU-4 assessment but did not have any HCV RNA assessment ≥ 70 days after the last dose of any study drug (ie, lower bound of FU-12 visit for HCV RNA data), the subject is categorized as having “With HCV FU-4 but No FU-12 and thereafter”.

In addition, the total number of subjects who were enrolled, and the number of subjects in each of the disposition categories listed above will be depicted by a flowchart.

The following by-subject listings will be provided by region and subject ID number in ascending order to support the above summary tables:

- Disposition for subjects who complete study treatment and study

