6.2.2. Analysis Methods for Secondary Efficacy Endpoints

For analyses of HCV RNA < LLOQ by visit while on treatment and during the posttreatment (SVR) follow-up period, subjects will be assigned a value at each visit based on the analysis visit windows specified in Section 3.7.2. Missing values will be imputed based on the categorical imputation rules described in Section 3.4.1. The two-sided 95% exact confidence interval based on Clopper-Pearson method will be provided for the percentage of subjects with HCV RNA < LLOQ at each visit by region and genotype. The overall category for “HCV RNA < LLOQ” will be split into the following 2 subcategories: “< LLOQ TND” for subjects with target not detected and “< LLOQ detected” for subjects with < LLOQ detected in tabular displays.

Graphs for the percentage of subjects with HCV RNA < LLOQ over time during treatment will be displayed.

Summary statistics will be presented for absolute values and change from baseline in HCV RNA (\log_{10} IU/mL) by visit through EOT. Imputation rules described in Section 3.4.1 will be used to assign HCV RNA values for missing values at a visit that are bracketed by “< LLOQ TND” and/or “< LLOQ detected”. Otherwise, a missing = excluded analysis will be performed. Plots of the mean \pm SD and median (Q1, Q3) of absolute values and changes from baseline in HCV RNA through EOT will be presented.

For the SVR12 endpoint analysis, a summary table of the number and percentage of subjects with SVR12, virologic failure (VF), and Other by region and genotype will be created. All subjects who achieve SVR12 will be categorized as SVR12. Virologic failure will be descriptively summarized as “on-treatment virologic failure” and relapse (which will be broken down by study drug completed yes/no). Subjects who do not achieve SVR12 and do not meet criteria for VF will be categorized as “Other”. The denominator for relapse will be the number of subjects who had HCV RNA < LLOQ on their last observed on-treatment HCV RNA measurement; otherwise, the denominator will be the number of subjects in the FAS.

[figure not shown]
A concordance table between SVR12 and SVR24 will be provided by region and genotype. Subjects with both observed SVR12 and observed SVR24 data will be included for this analysis.

Drug resistant substitutions will be analyzed and presented as part of the Clinical Study Report.

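### Does carrying SVR12 success forward to a missing SVR24, with no table row for the imputed subjects, undermine the SVR24 result?

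*SAP*

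**What the plan says.** Section 3.4.1 sets the general rule for categorical HCV RNA: "If a data point is missing and is not bracketed, the missing data point will also be termed a failure". SVR24 is the one exception; it takes the subject's SVR12 status. For responders this means: "Success for SVR12 who have no further HCV RNA measurements collected will be counted as a success for SVR24". The reason given is the high correlation between the two endpoints.

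Section 6.2.2 applies this to the by-visit analysis: "Missing values will be imputed based on the categorical imputation rules described in Section 3.4.1". It adds an interval: "The two-sided 95% exact confidence interval based on Clopper-Pearson method will be provided for the percentage of subjects" below LLOQ at each visit, by region and genotype. The tables split results below LLOQ into target not detected and detected, not into observed and imputed.

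The same section plans a check on the rationale: "A concordance table between SVR12 and SVR24 will be provided by region and genotype". Its population is restricted: "Subjects with both observed SVR12 and observed SVR24 data will be included for this analysis".

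Sections 3 and 3.6 commit the study to by-subject listings of collected data for the Safety Analysis Set, sorted by region, subject and visit date. Section 4.1 tabulates subjects without HCV RNA from FU-4 or from FU-12 onward, and study non-completers: "Did not complete the study with reasons for premature discontinuation of study". It has no row for subjects with an FU-12 value but none at FU-24.

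**The concern.** For every other post-treatment visit, an unbracketed missing value lowers the response rate. For SVR24, a responder lost after Week 12 stays a success, so such loss cannot pull the rate down, and the exact interval treats the carried value like a measured one. The concordance table leaves out the very subjects whose value was carried. The non-completion rows are not limited to SVR12 responders, and note i to Appendix 1 releases relapsed subjects from later visits, so those rows mix relapse with loss.

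The proportion with SVR24 is a stated secondary objective (Section 1.1). If many responders missed Week 24, the reported rate would largely repeat SVR12, and the reader would want to know how much of it was measured and how low it could be.

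**Working it through.** **The plan's own figures.** The SAP states no number for SVR24 imputation. Its related figures reproduce. The exact test in Region 1 (260 subjects, 91% against 85%) rejects upward at 233 or more responders, with power 81.5% against the stated more than 80%. The four Clopper-Pearson intervals in Section 1.3 come out at 70.8-87.3, 82.4-95.1, 75.5-84.0 and 86.4-92.9; all agree with the SAP (the third lower limit is 75.49 before rounding).

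**Inputs.** From the SAP: N = 360 overall, 260 in Region 1, 100 in Region 2. Assumed, because the SAP gives none of them: SVR12 of 95%; about 2%, 5% or 10% of responders imputed (m); late relapse r of 0.5% to 10% among those imputed.

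**Likely overstatement.** Error in points = 100 × m × r / N.

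| Population | SVR12 responders | m | Error, r = 0.5% to 10% |
|---|---|---|---|
| Overall | 342/360 | 7, 17, 34 | 0.01-0.19, 0.02-0.47, 0.05-0.94 |
| Region 1 | 247/260 | 5, 12, 25 | 0.01-0.19, 0.02-0.46, 0.05-0.96 |
| Region 2 | 95/100 | 2, 5, 10 | 0.01-0.20, 0.03-0.50, 0.05-1.00 |

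The largest value needs both 10% loss and 10% late relapse among those lost: 100 × 10 × 0.10 / 100 = 1.00.

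Suppose instead that subjects who do not return resemble those who do, and that no late relapse is observed. A cautious r is then the upper 95% exact limit of 0 out of the returners. With 10% imputed:

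- Overall: 0/308 gives 1.19%; 34 × 1.19 / 360 = 0.11 points.
- Region 1: 0/222 gives 1.65%; 25 × 1.65 / 260 = 0.16 points.
- Region 2: 0/85 gives 4.25%; 10 × 4.25 / 100 = 0.42 points.

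These are confidence limits, not maxima.

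**Worst case.** Count every imputed responder as a failure, with no observed late relapse. Overall, 342/360 = 95.0% (92.2-97.0) becomes:

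- 335/360 = 93.1% (89.9-95.5) with 7 imputed;
- 325/360 = 90.3% (86.7-93.1) with 17;
- 308/360 = 85.6% (81.5-89.0) with 34.

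This is a bound: it supposes that all the missing responders relapsed.

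**Can the reader see the imputed number and a bound from what is planned?**

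1. *Listings.* Sections 3.1.2 and 3.1.3 define the FAS and the Safety Analysis Set identically, so the listings cover everyone in the SVR24 denominator. The FU-12 window is Days 70-146 and FU-24 is Days 147-210 (Table 3-2), with no gap between them. Section 3.7.3 takes the closest record for other visits, "except for HCV RNA posttreatment follow-up visits, for which the latest record in the analysis window will be selected". An SVR12 responder with no further sample is therefore one with no HCV RNA after FU Day 146. A dated HCV RNA listing allows that count.
2. *Concordance table.* Subjects with success observed at both times, divided by the FAS, can only be too low as a bound, never too high. SVR12 successes minus the SVR12-success row is an upper limit on the number imputed. It overcounts only bracketed SVR12 successes, who have no sample on any of the 77 days from 70 to 146 and then return, and responders whose only later sample falls after Day 210, 42 days past nominal Day 168. With 7 imputed and 1 such subject, the table gives 342 − 8 = 334, or 334/360 = 92.8%, against a true bound of 93.1%. With 5 such subjects it gives 330/360 = 91.7%. Both err on the cautious side.

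**What the rule does not touch.** The exception is confined to SVR24. SVR12 keeps missing as failure, so a subject lost before FU-12 counts as a failure there and, by the same carry-forward, at SVR24. The Region 1 test in Section 6.1 is unaffected.

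**The case for a change.** The strongest case is that transparency about imputation should not depend on a reader tallying listings or subtracting one table from another. The imputed count requires no assumption about outcome, costs one row, and would sit naturally beside the FU-4 and FU-12 rows in Section 4.1. The concordance table tests the correlation only among those who came back, and cannot show how many did not. In small genotype columns a few subjects matter: in a group of 60 with 57 responders, 3 imputed move the worst-case bound from 95.0% to 54/60 = 90.0%.

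The facts in this stand: no visible table labels imputed SVR24 successes, and no worst-case rate is planned. What does not follow is that the plan is wrong. The rule is explicit, its reason is stated, and nothing elsewhere in the SAP contradicts it. The small-group figure is a bound that requires every missing responder to have relapsed. The extra row would be a courtesy to the reader and would change neither the SVR24 rate nor any conclusion drawn from it.

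**Conclusion.** The concern does not hold. The SAP fixes the SVR24 rule in advance, gives its reason, plans a check of that reason, and provides outputs from which the imputed number can be counted or conservatively bounded. Under the assumed ranges the overstatement is 0.01 to 0.94 points overall and at most 1.00 point in any region, on an endpoint with no hypothesis test.

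This rests on three things: assumed loss and late-relapse rates, since the SAP gives none; the general listing commitment covering HCV RNA, which Section 6.2.2 does not name separately; and the visible text only, because one figure in Section 6.2.2 is not shown and Section 6.3 is redacted. Much heavier loss after Week 12 would widen the worst-case bound, but it would show in the listings and in a thin concordance table.

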3.4.2. Outliers

Outliers will be identified during the data management and data analysis process, but no sensitivity analyses will be conducted. All data will be included in the data analysis.

3.5. Multiple Comparisons

No multiplicity adjustment will be made.

3.6. Data Handling Conventions and Transformations

By-subject listings will be presented for all subjects in the Safety Analysis Set and sorted by region, subject ID number, visit date, and time (if applicable) unless otherwise specified. Data collected on log forms, such as AEs, will be presented in chronological order within subject.

Age (in years) on the date of the first dose of study drug and sex at birth will be used for analyses and presentation in listings.

If a subject was not dosed with study drug at all, then the date the informed consent was signed will be used instead of the first dose date of study drug. For some countries, only birth year is collected on the CRF. In those cases, “01 January” will be used for the unknown birth day and month for the purpose of age calculation, unless age is captured on the CRF.

Non-PK data that are continuous in nature but are less than the lower limit of quantitation or above the upper limit of quantitation will be imputed as follows:

- A value that is one unit less than the limit of quantitation will be used for calculation of descriptive statistics if the datum is reported in the form of “< x” (where x is considered the limit of quantitation). For example, if the values are reported as < 50 and < 5.0, values of 49 and 4.9, respectively, will be used for calculation of summary statistics. An exception for this rule is any value reported < 1. For the values reported as < 1 or < 0.1, value of 0.9 or 0.09 will be used for calculation of summary statistics.

- A value that is one unit above the limit of quantitation will be used for calculation of descriptive statistics if the datum is reported in the form of “> x” (where x is considered the limit of quantitation). Values with decimal points will follow the same logic as above.
- The limit of quantitation will be used for calculation of descriptive statistics if the datum is reported in the form of “≤ x” or “≥ x” (where x is considered the limit of quantitation).

The COBAS[®] TaqMan[®] HCV Quantitative Test, v2.0 was used to determine HCV RNA results in this study. The lower limit of quantitation (LLOQ) of the assay is 15 IU/mL.

When the calculated HCV RNA value is within the linear range of the assay, then the result will be reported as the “<< numeric value>> IU/mL”. This result will be referred to in this document as the numeric result or as “≥ LLOQ detected” for categorical result.

When HCV RNA is not detected, the result is reported as “No HCV RNA detected” or “target not detected”. This result will be referred to in this document as “< LLOQ target not detected” or “< LLOQ TND”.

When the HCV RNA IU/mL is less than LLOQ of the assay, the result is reported as “< 15 IU/mL HCV RNA detected”. This result will be referred to in this document as “< LLOQ detected”.

The overall category of HCV RNA < LLOQ includes “< LLOQ TND” and “< LLOQ detected.”

For numerical HCV RNA data, values below LLOQ will be set to the LLOQ – 1 IU/mL (ie, 14 HCV RNA IU/mL). HCV RNA values returned as “No HCV RNA detected” will also be set to 14 IU/mL.

For selected analyses, HCV RNA data (IU/mL) will be transformed to the logarithmic (base 10) scale (\log_{10} IU/mL).

